### 5.6.3. Part B

A DEC meeting based on all available safety, tolerability and PK data accumulated from Part A of the study and the dose modification / stopping criteria will be used to decide:

- The progression to Part B
- The starting dose level of Cohort 4
- The dosing regimen of Part B
- Whether dosing will be in a fed or fasted state

The decision for the next repeat dose level Cohorts (Cohort 5 onwards) will be made at a DEC meeting following completion of a minimum 10 days dosing in no fewer than 4 or more participants from the previous repeat dose cohort and will be based on:

- assessment of safety, plasma GSK3186899 PK concentrations obtained from a minimum of 4 or more participants from the previous repeat dose cohort. Individual safety data (AEs, laboratory safety tests, ECGs and vital signs) will be reviewed.
- evaluation of all available safety, tolerability and PK data accumulated from the previous repeat dose cohort.

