## 2.2. PART B (Cohorts 4-6)

Procedure	Screening (Up to 28 days before Day 1)	Study Period (Days)													Follow-up (14-21 days post last dose) / Early Withdrawal	Notes	
		-2	-1	1	2	3	4	5	6	7	8	9	10	11	12		
Outpatient Visit	X															X	
Admission to Clinical Unit		X															
Inpatient Stay at Clinical Unit			←-----X-----→														
Discharge from Clinical Unit																X	Following completion of all assessments.
Informed Consent	X																
Inclusion and Exclusion Criteria	X																
Demography	X																
Full Physical Examination	X																Additional exams/screens may be performed, or brief exams can be made into full exams, by the Investigator, as deemed necessary (e.g. where safety or laboratory findings indicate). Tests will be conducted within site specified standards.
Brief Physical Examination			X	X				X					X	X			
Drug/Alcohol/Smoki ng Screen	X		X														Tests include alcohol breath test, smoking breath test and urine drug screen.
Medical/Medication/ Drug/Alcohol History	X																
HIV, Hepatitis B and C Screening	X																
FSH + Oestradiol	X																Females only, if required
Holter Monitoring (48 hour)	X																

Procedure	Screening (Up to 28 days before Day 1)	Study Period (Days)													Follow-up (14-21 days post last dose) / Early Withdrawal	Notes		
		-2	-1	1	2	3	4	5	6	7	8	9	10	11	12	13		
Haematology/ Clinical Chemistry /Urinalysis Test	X		X		X		X		X		X		X		X		X	If trace protein is detected, a repeat test can be performed.  Sample to be drawn pre-dose on Days 2, 4, 6, 8 and 10.  Non-fasted samples can be collected on Day -1 and Follow-Up Visit. All other samples to be collected in fasted state.
Cortisol Test			X											X			Tests to be performed in the early morning on Day -1 and Day 11. If levels are <420 nmol/L, then a adrenocorticotropic hormone (ACTH) stimulation test will be performed to assess hypothalamic pituitary adrenal (HPA) axis.	
Safety biomarkers (KIM1, NGAL, Urinary albumin)				X				X									First urine sample of the morning to be collected (pre-dose). Additional samples may be collected, as deemed necessary by the Investigator (e.g. where safety or laboratory findings indicate).	
Telemetry				X	X												Continuous at least 24 hr post-evening dose. Initiate at least 15 min. prior to dosing.	
Randomization				X														

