	
for 7 days (mean AUC 204 µg.h/mL on Day 7).
 
 
• This test article-related, non-adverse finding correlated with increased adrenal weight following 28 days dosing in male rats given ≥100 mg/kg/day, as SDD, and female rats given ≥25 mg/kg/day, as SDD.
 
	
Therefore, no specific monitoring, other than standard clinical and laboratory parameters, will be implemented for healthy volunteers during SAD part of the study. However, for the MAD cohorts, adrenal function will be assessed prior to first dose and on completion of 10 days dosing. Also, by observing the safety margin for renal findings of up to 3-fold (during the SAD part of the study) and up to 5-fold (during the MAD part of the study) for the total daily AUC and <math>C_{max}</math> to be below the female rat NOAEL (AUC: 434 µg.h/mL, <math>C_{max}</math>: 46.2 µg/mL), should reduce the risk of adrenal and ovary effects in humans.
 
Exclusion criteria (Part B only):
 
 
• Participants with borderline adrenal glucocorticoid function (early morning serum cortisol < 420nmol/L) will only be included in the study if after an adrenocorticotropic hormone (ACTH) stimulation test, there is a rise in cortisol level from baseline of at least 250nmol/L
 
 
Monitoring:
 
 
• Participants will be monitored clinically for any symptoms of adrenal insufficiency, (nausea, vomiting, dizziness) and objective assessments (supine/standing BP). Depending on the investigators clinical judgement, a ACTH
 

Potential Risk of Clinical Significance	Summary of Data / Rationale for Risk	Mitigation Strategy
		
stimulation test may be done to exclude adrenal insufficiency.
 
Day 11 (Part B only):
 
 
• Early morning serum cortisol (+ ACTH stimulation test if levels < 420nmol/L) will be performed on all participants at Day 11. If during Day 11 early morning cortisol is < 420 nmol/L, volunteers will undergo a ACTH stimulation test the next day to rule out adrenal insufficiency. Participants with adrenal insufficiency will be withdrawn from the study, refer to Section 8.1.4.
 
 
Stopping criteria:
 
 
• A stopping criterion has been included if one or more volunteers in Part B develop adrenal insufficiency with clinical signs and symptoms.
 

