**Table 2 Study Duration of Cohorts 4-6**

Screening	All screening assessments to be completed within 28 days prior to first-dose.
Treatment Period	Each Cohort will consist of a 10-day treatment duration (Days 1-10), with participants in-house for 14 nights and 15 days. Participants will be admitted to the unit the day before dosing (Day -2) and will remain in the unit overnight until Day 13, when they will be discharged after completion of all assessments.
Follow-up	At least 14 days and no greater than 21 days after last study drug administration. If warranted, additional follow-up visits may be scheduled.
Total duration	Approximately 8-9 weeks

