### 5.6.2. Part A

**Dose escalation meeting:** The decision to proceed to the next dose level of GSK3186899 will be made at a DEC meeting based on:

- all available safety and tolerability data from a minimum of 48 hours post-dose from a minimum of 4 or more participants who have received GSK3186899 at the current dose level. Individual safety data (AEs, laboratory safety tests, telemetry, ECGs and vital signs) will be reviewed.
- all available safety and tolerability data accumulated from preceding dose levels and available PK data from current (minimum of 4 or more participants) and preceding dose levels.

**Safety review meeting:** The decision to proceed from Cohort 1 Period 4 (DL4) to Cohort 2 Period 1 (DL4), and Cohort 3 Period 1 (DLX) to Cohort 3 Period 2 (DLX-FD) will be made by the Principal Investigator and Medical Monitor based on:

- all available safety and tolerability data from a minimum of 48 hours post-dose from a minimum of 4 or more participants who have received GSK3186899 at the current dose level. Individual safety data (AEs, laboratory safety tests, telemetry, ECGs and vital signs) will be reviewed.

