### **8.1.1. Dose Adjustment/Stopping Pharmacokinetic Criteria**

The following dose adjustment / PK stopping criteria will apply:

- A maximum  $C_{max}$  of 15.4 $\mu$ g/mL or 9.24 $\mu$ g/mL and a total daily AUC of 145  $\mu$ g.h/mL or 86.8  $\mu$ g.h/mL for SAD or MAD part, respectively, will not be intentionally exceeded and will be used as safety threshold exposures for PK stopping criteria as per GSK renal safety panel recommendations. These exposures are 3-fold or 5-fold below the NOAEL exposures of 46.2  $\mu$ g/mL for  $C_{max}$  and 434  $\mu$ g.h/mL for total daily AUC in the 28-day female rat study for SAD or MAD part, respectively.
- Dose escalation will be stopped if any single participant reaches exposures greater than PK stopping criteria threshold exposures. We intend to use the PK dose escalation rule for progression to the next dose or dose adjustment which will involve establishing a relationship between dose vs. exposures ( $AUC_{0-24h}$  &  $C_{max}$ ) using a power model and linear mixed effect modeling once PK data are available from a minimum of two prior dose levels. This model will be continually updated with incorporation of new dose levels as they become available. This developed model will be used to project mean  $AUC_{0-24h}$  and  $C_{max}$  for the next dose level.
- If mean group exposure from the maximum total daily dose is predicted to reach the PK stopping criteria exposures, dose escalation will be stopped, or dose adjustment will be planned, as appropriate. For any dose adjustments for the next dose, an increase or decrease in the nominal dose will occur if the projected exposure for the

next dose deviates by more than 30% of the initial projected mean systemic exposure. The GSK study team will decide based on emerging safety, tolerability and PK information whether to evaluate any lower doses or repeat doses already evaluated in remaining periods to collect additional safety and PK data.

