3.1.1.1. Dose escalation meetings

Statistical displays will not be produced by Biostatistics for the dose escalation meetings. During the meeting, safety data (presented by the CUC Principal Investigator or delegate) and PK data (presented by Study Pharmacokineticist or delegate) will be reviewed by the committee.

The meeting will discuss blinded data in an open forum with the GSK Study team members and Principal Investigator (or their delegate) in attendance. If required, the data may be reviewed in an unblinded fashion by the unblinded members including the SMG (formally GCSP) Safety representative and Study Pharmacokineticist.

The decision to proceed to the next dose level of GSK3186899 will be made at a DEC meeting based on:

- all available safety and tolerability data from individuals (including AEs, laboratory safety tests, telemetry, ECGs and vital signs) from a minimum of 48 hours post-dose (10 days for repeat dose) from a minimum of 4 or more participants who have received GSK3186899 at the current dose level

- all available safety and tolerability data accumulated from preceding single/repeat dose levels and available PK data from current (minimum of 4 or more participants) and preceding single/repeat dose levels.

Further details of the DEC membership, data to be reviewed and stopping criteria are outlined in the DEC charter.

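### Escalation to the next repeat-dose cohort does not wait for the Day 11 cortisol and any triggered ACTH result, a small gap that one sentence would close

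*Protocol*

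**What the plan says.** Protocol 5.6.3 sets the condition for starting Cohorts 5 and 6. The DEC meets "following completion of a minimum 10 days dosing in no fewer than 4 or more participants from the previous repeat dose cohort". It looks at safety and plasma concentrations from at least four participants, at individual adverse events, safety laboratory tests, ECGs and vital signs, and makes an "evaluation of all available safety, tolerability and PK data accumulated from the previous repeat dose cohort". Cortisol and ACTH are not named.

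SAP 3.1.1.1 restates the condition with "10 days for repeat dose) from a minimum of 4 or more participants who have received GSK3186899 at the current dose level". The Part A counterpart, Protocol 5.6.2, asks for data "from a minimum of 48 hours post-dose from a minimum of 4 or more participants who have received GSK3186899 at the current dose level". Protocol 5.6.3 does not say that the four must have received active drug.

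On adrenal testing, the Part B schedule (Protocol 2.2) has "Tests to be performed in the early morning on Day -1 and Day 11". If the Day 11 value is below 420 nmol/L, Protocol 3.3.1 says that "volunteers will undergo a ACTH stimulation test the next day to rule out adrenal insufficiency". Table 7 lists cortisol among the required safety laboratory assessments. Section 8.1.4 defines adrenal insufficiency as cortisol below 420 nmol/L with a rise after ACTH that does not exceed 250 nmol/L. Section 8.1.2 stops dosing only if such a participant also has compatible clinical signs or symptoms. Section 5.6.1 leaves the details of the data reviewed to the DEC charter, which is not among the documents.

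**The concern.** Protocol 3.3 says that adrenal monitoring was added because of the rat adrenal findings, and 3.3.1 schedules it for the repeat-dose cohorts only. The Day 11 test comes after a participant's last dose, so its result cannot reduce that participant's own exposure. Its main protective use is for later dosing, above all the next and higher cohort. Yet the condition for raising the dose can be met on Day 10, before the test is drawn.

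The stopping rule in 8.1.2 does not fully cover this. It acts only once the result is known, and a participant with abnormal biochemistry but no symptoms does not trigger it. For such a participant, committee review is the main safeguard before escalation, and nothing in 5.6.3 or SAP 3.1.1.1 ensures that the result exists when the committee meets.

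**Working it through.** The plan gives no figure to reproduce, so the check is a timeline.

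**Inputs**
- Each Part B cohort has 6 active and 2 placebo participants. The first two, one active and one placebo, are sentinels, and the other six may start after the sentinels' first 5 days of dosing (Protocol 5.1; SAP 2.3).
- Dosing is on Days 1 to 10, cortisol on Day 11 and any triggered ACTH test on Day 12 (Protocol 2.2 and 3.3.1).
- Admission is on Day -2 (Protocol Table 2). With no Day 0, first dose falls 2 days after admission.
- Assumption: the next cohort is admitted on the day of the decision. This is the normal order but is not expressly required.

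**Step 1: earliest dates, counted in the sentinels' study days.** The other six start no earlier than Day 6. Their Day 10 is 6 + 9 = 15, their Day 11 is 16 and their Day 12 is 17. Two sentinels cannot supply four participants, so Day 15 is the earliest date on which the 5.6.3 condition can be met.

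**Step 2: what exists at the decision.** Only the active sentinel is ahead of the other five active participants.

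| Decision | Active with cortisol drawn | Active past the ACTH day | Next cohort's first dose | Days from cortisol draw to first dose | Days from ACTH day to first dose |
|---|---|---|---|---|---|
| Day 15 | 1 of 6 | 1 of 6 | 15 + 2 = 17 | 17 - 16 = 1 | 17 - 17 = 0 |
| Day 16 | 6 of 6 | 1 of 6 | 16 + 2 = 18 | 18 - 16 = 2 | 18 - 17 = 1 |
| Day 17 | 6 of 6 | 6 of 6 | 17 + 2 = 19 | 19 - 16 = 3 | 19 - 17 = 2 |

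Laboratory turnaround is not stated, so the last two columns are upper limits on the time available to report and review a result.

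**Step 3: who could be dosed early.** If the next cohort's sentinels start on Day 17, its other six start no earlier than 17 + 5 = Day 22. That is 22 - 16 = 6 days after the previous cohort's cortisol draw and 22 - 17 = 5 days after its ACTH day. Exposure ahead of the results is therefore mainly one active sentinel, for a short time.

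**Step 4: size of the dose step.** Protocol 5.5.5 plans 0.5X, 0.75X and 1X. Taking X as the same dose throughout, the steps are 0.75/0.5 = 1.5-fold and 1/0.75 = 1.33-fold.

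**Step 5: how much the results could show.** The documents give no adrenal event rate. For an assumed true rate p, the chance of at least one case in n active participants is 1 - (1 - p)^n. For p = 5%, 10%, 20% and 30% this is 18.5%, 34.4%, 59.0% and 76.0% with n = 4, and 26.5%, 46.9%, 73.8% and 88.2% with n = 6. The results are informative but no guarantee of detection.

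**The case against.** The case for leaving the text alone is substantial.

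- **Cortisol is already within the review.** It is a required safety laboratory test in Table 7, 5.6.3 says that individual safety laboratory tests will be reviewed, and 8.1.8 has the DEC review laboratory abnormalities regularly. This stands: a reader might infer that the committee may disregard adrenal results, and the documents do not support that. What is missing is only a requirement that the Day 11 and Day 12 results exist at the meeting.
- **PK will usually delay the decision.** Day 10 exposure forms part of the stopping criteria (5.5.5), and under 8.1.1 "Dose escalation will be stopped if any single participant reaches exposures greater than PK stopping criteria threshold exposures". With twice-daily dosing, the last Day 10 sample is at 12 hours and cortisol is drawn the next morning. A Day 15 decision would need assay and derivation overnight. This largely stands, but it is inference: 5.6.3 does not ask for Day 10 PK by name, and no assay time is given.
- **Sentinel dosing limits exposure.** A reader might infer that the next cohort's 5-day sentinel review leaves the gap open, because it precedes those sentinels' own Day 11 test. But the missing results are the previous cohort's, and both test days will have passed before the remaining six start.
- **The hazard is modest.** The rat findings were judged non-adverse, repeat-dose exposure is held 5-fold below the NOAEL, and symptoms may prompt an earlier ACTH test. All of this stands and limits the harm.
- **Part A is a weak comparison for follow-up time.** After a single dose, post-dose follow-up is the only safety window, whereas Part B has 10 days of observation on drug. This stands. The comparison is useful only for the active-drug condition.
- **The charter may already contain the requirement.** It may, and the fix allows for it.

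**Conclusion.** The gap is real but small. The 5.6.3 condition can be met 1 day before the cortisol draw and 2 days before any triggered ACTH test, and neither 5.6.3 nor SAP 3.1.1.1 makes the decision wait. The realistic consequence is one active sentinel starting a 1.33- to 1.5-fold higher dose before a biochemical-only signal in the previous cohort is known. This is a cheap improvement to make, not a major defect.

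Two stronger readings are not supported. A reader might infer from the Day 15 row that escalation would typically rest on adrenal data from 1 of 6 active participants. That needs a decision with no lag at all, which the PK requirement makes unlikely. A reader might also infer that the four counted participants could include only 4 - 2 = 2 on active drug. Section 5.6.3 on its own does not exclude this, but it would take staggering or dropout that the timeline does not assume, and SAP 3.1.1.1 already requires receipt of GSK3186899. The omission in 5.6.3 is an inconsistency to correct.

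The conclusion assumes that admission follows the decision and that the charter adds no condition. SAP 3.1.1.1 could be read as asking for 10 days of data after dosing, which would cover both tests, but 5.6.3 speaks of 10 days of dosing.

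**What to change.** Add one sentence to Protocol 5.6.3 and mirror it in SAP 3.1.1.1: *before the first dose in the next repeat-dose cohort, the DEC will have reviewed the Day 11 cortisol result, and any ACTH stimulation result it triggers, for at least 4 participants who received GSK3186899 in the previous cohort.* If the DEC charter already requires this, cite it in 5.6.3 instead. Either way, state in 5.6.3 that the four received active drug.

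No new sample or visit is needed. The tests are already scheduled and fall within the in-house stay: "Participants will be admitted to the unit the day before dosing (Day -2) and will remain in the unit overnight until Day 13". The unblinded DEC members (5.6.1) can confirm that four received active drug without wider unblinding. The delay is at most 1 to 2 days plus laboratory turnaround at each of the two escalations (Cohort 4 to 5 and Cohort 5 to 6), and possibly none where PK turnaround already sets the timing.

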## 6. STUDY POPULATION

Prospective approval of protocol deviations to recruitment and enrolment criteria, also known as protocol waivers or exemptions, is not permitted.

### 6.1. Inclusion Criteria

Participants are eligible to be included in the study only if all of the following criteria apply:

AGE
1. Participant must be 18 to 55 years of age inclusive, at the time of signing the informed consent.

TYPE OF PARTICIPANT AND DISEASE CHARACTERISTICS
2. Healthy as determined by the Investigator or medically qualified designee based on a medical evaluation including medical history, physical examination, laboratory tests and cardiac monitoring.  A subject with a clinical abnormality or laboratory parameter(s) which is/are not specifically listed in the inclusion or exclusion criteria, outside the normal reference range for the population being studied may be included only if the Investigator in consultation with the Medical Monitor (if required) agree and document that the finding is unlikely to introduce additional risk factors and will not interfere with the study procedures.  Note: Screened subjects with laboratory values outside of the normal range may be repeated once for inclusion into the study at the discretion of the Investigator.

WEIGHT
3. Body weight $\geq$ 50 kg and body mass index (BMI) within the range 18.5 - 28 kg/m  (inclusive).

SEX

4. Male and/or Female Subjects
 
a. Male participants: A male participant with a female partner of reproductive potential must agree to use contraception as detailed in Appendix 4 of this clinical study protocol during the treatment period and for at least 90 days after the last dose of study treatment and refrain from donating sperm during this period.
 
b. Female participants: A female participant is eligible to participate if she is not a woman of childbearing potential (WONCBP) as defined in Appendix 4.

INFORMED CONSENT

5. Capable of giving signed informed consent as described in Appendix 1, which includes compliance with the requirements and restrictions listed in the ICF and in this protocol.

## 6.2. Exclusion Criteria

Participants are excluded from the study if any of the following criteria apply:

MEDICAL CONDITIONS

 
1. History or presence of or current cardiovascular, respiratory, hepatic, renal, gastrointestinal, endocrine, hematological, or neurological disorders capable of significantly altering the absorption, metabolism, or elimination of drugs; constituting a risk when taking the study treatment; or interfering with the interpretation of data.
 
2. Previous history of leishmaniasis
 
3. Alanine transaminase (ALT) <math>>1.5 \times</math> upper limit of normal (ULN).
 
4. Bilirubin <math>>1.5 \times</math> ULN (isolated bilirubin <math>>1.5 \times</math> ULN is acceptable if bilirubin is fractionated and direct bilirubin <math><35\%</math>).
 
5. Current or chronic history of liver disease, or known hepatic or biliary abnormalities (with the exception of Gilbert's syndrome or asymptomatic gallstones)
 
6. Current or past history of clinically significant gastritis or gastroduodenal ulcers or regular use of non-steroidal anti-inflammatory drugs (NSAID)
 
7. QTc <math>>450</math> msec
 
 
NOTES:
 
 
• The QTc is the QT interval corrected for heart rate according to Bazett's formula (QTcB), Fridericia's formula (QTcF), and/or another method, machine-read or manually over-read.
 
• The specific formula that will be used to determine eligibility and
 

**MEDICAL CONDITIONS**

discontinuation for an individual subject should be determined prior to initiation of the study. In other words, several different formulae cannot be used to calculate the QTc for an individual subject and then the lowest QTc value used to include or discontinue the subject from the trial.

- For purposes of data analysis, QTcB, QTcF, another QT correction formula, or a composite of available values of QTc will be used as specified in the Reporting and Analysis Plan (RAP).

